The study subjects' neck and décolletage area will be divided into two equal halves. The line of division will be from the mid mental protuberance to manubriosternal junction. One half of the neck and upper chest area will be treated with ablative fractional CO2 laser while the other half will be untreated and used as a control. If desired after the study endpoint, patients may have the other side of their neck treated at no additional charge.

Primary Outcome Measures:

Physician's Global Aesthetic Improvement Scale at 12- and 24-weeks post treatment.

Photographs will be presented to a panel of independent dermatologists. The panel will be blinded to treatment parameters and the treatment laterality at each photograph time point. Each

²⁶ Ramsdell WM. Fractional carbon dioxide laser resurfacing. *Semin Plast Surg.* 2012;26(3):125-130. doi:10.1055/s-0032-1329414

²⁷ Omi T, Numano K. The Role of the CO2 Laser and Fractional CO2 Laser in Dermatology. *Laser Ther.* 2014;23(1):49-60. doi:10.5978/islsm.14-RE-01

dermatologist will be asked to identify the baseline and post-treatment images from randomized, paired images for all subjects. Reviewers will rate improvement in POC in 10% increments on a 10-point scale (0% no improvement to 100% or complete clearance)

Secondary Outcome Measures

Subject Satisfaction Assessment at 12- and 24-weeks post treatment. Subjects will assess overall satisfaction with improvement of poikiloderma of civatte using an 5-point satisfaction and aesthetic scale.

Study subjects will be followed for 24 weeks post-laser treatment to assess incidence and severity of all procedure-related adverse events.

4. Study procedures

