Given the current pandemic, limited in-person follow-ups will be scheduled (once at baseline before treatment, then at 12 and 24-weeks post-treatment. Participants will communicate immediate post-treatment issues or concerns along with selfies through MyChart on day 2, 3, 7, 10, 14 to track progress and to identify any post procedural complications in a timely fashion. There will also be no costs to the patients for the laser procedures as funding will be supplied by the UT Southwestern Dermatology department via an educational grant. Patients desiring treatment of the control side after the study end-point (24 weeks) will be provided at no cost for the participants.

5. Sub-Study Procedures: N/A

6. Criteria for Inclusion of Subjects

- Male and female subjects, English and non-English speakers, and subjects more than 18 years old
- Clinical diagnosis of poikiloderma of Civatte affecting the neck and chest

- Agree to not undergo any other procedures on the neck and chest area during the study
- Agree to refrain from tanning for 6 months post-procedure
- Willing and able to read, understand, and sign the consent form
- Willing and able to adhere to the treatment and follow-up schedule as well as post-treatment care

7. Criteria for Exclusion of Subjects

- Patients under 18 years old
- Active skin infection, dermatitis, or a rash on the treatment area
- Pregnant or lactating patients
- Patients on immunosuppressive medications
- Any laser procedures or chemical peel procedures on the neck or chest area within the past 6 months
- Patients with multiple comorbidities such as diabetes mellitus, cardiovascular diseases, neurologic disorders, internal malignancies
- Personal history or family history of forming keloids or hypertrophic scars, or abnormal wound healing
- Patients with known bleeding disorders or taking more than one anticoagulation medications
- Undergoing any surgery in the treatment area within the past 12 months
- History of radiation to the head, neck, and chest area
- Systemic use of isotretinoin within 6 months
- Any use of gold therapy
- Current smoker or history of smoking within 12 months of study

- Any physical or mental condition in which the investigators deem unsafe for the subject to participate in the study.
- History of recurrent herpes simplex on the neck or chest.

8. Sources of Research Material

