Descriptive statistics will be used to summarize patient demographics. Count (%) will be used for categorical variables; and mean, standard deviation (SD), and range (min/max) will be used to summarize continuous variables with approximately normal distributions. Skewed continuous variables will be summarized by median and interquartile range (IQR). Outcome data will be collected on patient satisfaction assessment scores and physician's global aesthetic improvement scores, as well as assessment of adverse events. The Wilcoxon signed rank test will be used to compare the magnitude of change between the baseline scores and post-intervention scores. The Wilcoxon signed rank test will also be used to compare the magnitude of change of the treated

area and the control area. A p-score of <0.05 will be considered statistically significant. The target sample size is 10 people.

Outcome Measurement:

Global Aesthetic Improvement Scale`

| | Degree | Description |
|---|-------------------------|--|
| 1 | Exceptional improvement | Excellent corrective result |
| 2 | Very improved patient | Marked improvement of the appearance, but not completely optimal |
| 3 | Improved patient | Improvement of the appearance, better compared with the initial condition, but a touch-up is advised |
| 4 | Unaltered patient | The appearance substantially remains the same compared with the original condition |
| 5 | Worsened patient | The appearance has worsened compared with the original condition |

Patient Satisfaction Assessment

| | | | | |
|--|--|--|---|--|
|  |  |  |  |  |
|  |  |  |  |  |
| Very Unsatisfied | Unsatisfied | Neutral | Satisfied | Very Satisfied |

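### Section 14 gives an ill-defined, uncontrolled before/after test the same standing as the randomised treated-versus-control test, and Section 3 describes a different scale from the named primary outcome

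*Combined protocol and SAP*

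**What the plan says.** Section 3, under Primary Outcome Measures, names the outcome as the physician's "Global Aesthetic Improvement Scale at 12- and 24-weeks post treatment". The procedure beneath that heading is a different rating: "Reviewers will rate improvement in POC in 10% increments on a 10-point scale (0% no improvement to 100% or complete clearance"). It is made by a blinded panel, and each "dermatologist will be asked to identify the baseline and post-treatment images from randomized, paired images for all subjects".

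Section 14 prints GAIS as five grades, from 1 (best) to 5 (worsened), so it runs in the opposite direction to the percent rating. Each grade is relative to the starting condition; grade 4, for example, reads "The appearance substantially remains the same compared with the original condition". Section 14 does not mention the percent rating.

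Two tests follow. The first: "The Wilcoxon signed rank test will be used to compare the magnitude of change between the baseline scores and post-intervention scores". The second: "The Wilcoxon signed rank test will also be used to compare the magnitude of change of the treated" area and the control area. One threshold covers both: "A p-score of <0.05 will be considered statistically significant". Neither test is called primary, no visit is chosen, and no p-value method or sidedness is given.

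Section 4 states that the treated side is chosen at random. It also requires daily sunscreen after the first week, and Section 6 requires no tanning for six months. Section 4 speaks of "Patients desiring treatment of the control side after the study end-point (24 weeks"), but only to say when the control half may be treated.

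**The concern.** The split-neck design with a randomised side exists to support one contrast, treated half against untreated half. Section 14 puts a before/after test beside it at the same threshold. That test is weaker in three ways.

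- **It has no defined input.** GAIS and the percent rating both measure change from baseline, and satisfaction is collected only at weeks 12 and 24. There is no baseline score. The test can be run only against an implied null value, such as 0% or GAIS grade 4.
- **It has no control.** The post-treatment sunscreen and tanning rules are not limited to the treated half, so both halves may change without any laser effect. The sunscreen month before the first visit precedes the baseline photographs and is not counted here.
- **On the percent scale it can point only one way.** No rating is below 0%, and the plan does not say how a pair is scored when the reviewer picks the wrong image as baseline.

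At stake is a report of success from a significant before/after result at either visit when the randomised comparison shows nothing.

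**Working it through.** **Inputs from the documents.** n = 10; p < 0.05 per test (two-sided assumed); two visits; two comparisons; the two scales above. The plan gives no error rate, power or effect size, so it has no figure to reproduce. As a reference, the exact signed-rank test with 10 untied differences has a two-sided level of 0.0488.

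**1. Percent scale, before/after, no negative ratings possible.** With k non-zero ratings, all positive, exact p = 2/2^k:

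- k = 5: 2/32 = 0.0625
- k = 6: 2/64 = 0.031

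So six non-zero ratings suffice, whatever their size. If each patient has an assumed chance q of a non-zero rating, the chance of significance at one visit is P(Binomial(10, q) ≥ 6). For q = 0.5 this is (210 + 120 + 45 + 10 + 1)/1024 = 386/1024 = 37.7%.

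| q (assumed) | one visit | either of two independent visits, 1 − (1 − p)² |
|---|---|---|
| 0.3 | 4.7% | 9.2% |
| 0.4 | 16.6% | 30.5% |
| 0.5 | 37.7% | 61.2% |

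The last column is an upper limit, because ratings at the two visits will be positively correlated.

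**2. Same scale, misidentified pairs scored as negative.** Under pure noise a reviewer picks the wrong image about half the time, so signs are symmetric. The chance of significance is then the sum over k of P(K = k) times the exact level with k untied non-zero values. Those levels are 0.0313, 0.0469, 0.0391, 0.0391 and 0.0488 for k = 6 to 10, and zero below 6. For q = 0.5: 0.2051×0.0313 + 0.1172×0.0469 + 0.0439×0.0391 + 0.0098×0.0391 + 0.0010×0.0488 = 0.014. For q = 0.3 and 0.4 the sum is about 0.002 and 0.006. Simulation gave about 0.2%, 0.6% and 1.5% for the three values of q.

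**3. GAIS tested against the unaltered grade, either visit, exact p (simulated).** Shares are worsened/unaltered/improved/very improved/exceptional, all assumed and the same on both halves.

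- 10/70/15/5/0: about 0.8%
- 10/50/25/10/5: 15–19%
- 20/40/20/15/5: between these two
- symmetric 20/60/20 (worsened/unaltered/improved): about 0.7–1.0%

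The higher values come from distributions with net improvement on both halves. They show how often the test detects a shared change, which is real but is not a laser effect.

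**4. Treated versus control, no laser effect.** 4,000 simulated trials per setting, with between-visit and between-side correlations of 0, 0.5 and 0.8 (assumed) and zero differences dropped.

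- Either visit counts, exact p: 0.1–7.1% on the percent scale, 0.1–5.5% on GAIS.
- Either visit counts, normal approximation without continuity correction: 3.4–9.7% and 4.0–9.1%.
- Week 24 only, exact p: at most 3.9%.

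In a separate simulation with normally distributed scores (100,000 trials), both halves improved equally by 0.25 to 1.0 SD. The one-visit treated-versus-control level stayed at about 4.9%. Shared change cancels in this comparison.

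**The case against.** The strongest reply is that the primary instrument is named. GAIS heads Section 3 and is the physician scale in Section 14, so the largest rates in step 1 concern a rating that Section 14 does not list for testing. That is fair. What stands is that the only panel procedure described yields percentages, so the plan does not say how a GAIS grade is produced or which rating is tested.

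Second, the before/after rates rest on assumptions. This also stands: one scoring rule for misidentified pairs moves the percent-scale rate roughly 25-fold at q = 0.5 (37.7% against about 1.5%), and the GAIS rate runs from about 1% to 19%. No single figure should be quoted.

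Third, a 10-patient study might be meant as exploratory. The documents do not say so: the stated purpose is to assess safety and efficacy, and a significance threshold is set.

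A reader might infer more than the documents support:

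- **That the sponsor plans to claim success from the before/after test.** No success rule is stated; the plan only leaves this open.
- **That 2 visits × 2 scales × 2 comparisons make eight tests, with a 33.7% chance of a false positive.** That figure assumes eight independent tests. These would be correlated, and Section 14 does not list the percent rating.
- **That testing two visits is itself a material error.** Step 4 shows that it adds little.

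**Conclusion.** The concern holds in a limited form. Section 14 gives equal standing to a before/after test that lacks a baseline score and a control, and to the randomised comparison the design was built for. It ranks neither the comparisons nor the visits. Section 3 names one scale and describes another.

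The rate of misleading before/after results is not determined by the documents:

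- Percent scale, one visit: 4.7–37.7% if 30–50% of patients get a non-zero rating and none can be negative; about 0.2–1.5% if misidentified pairs count as negative.
- GAIS against the unaltered grade, either visit: about 1–19%, the upper part reflecting shared improvement on both halves.

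For treated versus control, allowing either visit gives at most about 7% with exact p-values. All rates assume n = 10 with no dropout and two-sided tests. The rating distributions and correlations are assumed too. The design is sound; what needs repair is the definition and ranking of the tests.

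**What to change.** In Sections 3 and 14:

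- Name one primary test: the within-patient treated-versus-control comparison at week 24, by exact Wilcoxon signed-rank test at two-sided 0.05.
- Name one primary scale. GAIS is the natural default, because it is the named outcome and has a grade for worsening. State that the blinded panel rates each half separately and how reviewers' grades are combined.
- If the percent rating is chosen instead, score a misidentified pair as the negative of its rating. If the identification step is kept with GAIS, state how such a pair is graded.
- Make week 12 secondary, or test it only if week 24 is significant. Make the other rating secondary and report before/after results descriptively.
- If no confirmatory claim is wanted, say instead that all p-values are exploratory.

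The cost is a few sentences, with no added patients or visits. Section 3 does not say that each half is rated separately, so the panel may have more ratings to make from the planned photographs. An effect seen only at week 12, only before/after or only on the other rating could not be claimed as primary success. The exact test is also conservative on these coarse scales, with a level of at most about 4% in the settings examined.
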